8.4.1. Secondary SALT Endpoints

The following secondary SALT responder endpoints will be assessed:

- Percentage of patients achieving at least a 75% relative reduction in SALT score from Baseline at Weeks 12 and 24
- Percentage of patients achieving at least a 90% relative reduction in SALT score from Baseline at Weeks 12 and 24
- Percentage of patients achieving an absolute SALT score of ≤ 20 at Week 4
- Percentage of patients achieving an absolute SALT score of ≤ 10 at Week 24

In addition, the continuous secondary SALT endpoint of relative change in SALT score from baseline at Weeks 4, 8, 12, 16, 20, and 24 will be assessed with a MMRM. The model will include fixed factors for treatment group, study visit, and treatment by study visit interaction, with baseline SALT score as a covariate. Imputed values will not be used for the MMRM.

Relative reduction is based on relative change from baseline.

Relative change in SALT score is derived as percent change of the follow-up SALT score, where baseline SALT score is the denominator (i.e. absolute change divided by the baseline score, multiplied by 100).

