7.3. Method of Treatment Assignment and Blinding

Patients will be randomized in a 3:5:2 ratio (12 mg BID:8 mg BID:placebo). Randomization will be stratified by scalp hair loss into one of the following two categories: 1) Partial scalp hair loss (SALT ≥ 50 and < 95); 2) Complete or near-complete scalp hair loss (SALT ≥ 95). The randomization schedule will be generated prior to study start.

All study patients, Investigators, and site study staff will be blinded to study drug assignment for the duration of the study. Tablets and packaging of CTP-543 and placebo will be identical in appearance.

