Absolute and/or relative changes in SALT score, SPRO score, CGI-S and PGI-S values, BELA and BETA score, QPRO scores, and HADS anxiety and depression scores, will be assessed with a mixed effects repeated measures (MMRM) model. The model will include fixed factors for treatment group, study visit, and treatment by study visit interaction, with baseline SALT score as a covariate. Treatment group comparisons at each visit will be based on least squares mean estimates. An unstructured covariance structure will be used to model the within-subject errors. The Kenward-Roger approximation will be used to estimate denominator degrees of freedom.

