8.4. Secondary Endpoints

All statistical tests outside of the hierarchy defined in Section [8.1.4](#) and Figure 1 will be carried out at a two-sided significance level of ≤ 0.05 . Nominal p-values will be presented. Analyses will be performed using the Efficacy Population.

Missing values will not be imputed for efficacy endpoints which are not derived from SALT or SPRO scores.

For the secondary endpoints of proportions of patients achieving specified improvement criteria (hereinafter, “secondary responder endpoints”), pairwise treatment group differences from placebo at each scheduled evaluation will be assessed with the Cochran-Mantel-Haenszel test using baseline scalp hair loss as the stratification factor. Observed counts and percentages of responders will be summarized by treatment group and the p-values reported. Secondary responder endpoints derived from SALT or SPRO scores will be analyzed similarly to the primary endpoint according to Section [8.2.2](#).

For the secondary endpoints of absolute or relative changes (hereinafter, “continuous secondary endpoints”), treatment differences will be assessed with a mixed-effect model of repeated measures (MMRM). Model covariates are described in applicable sections below. Treatment group comparisons at each visit will be based on least squares (LS) mean estimates. An unstructured covariance matrix will be used to model the within-subject errors. Should the model fail to converge, an alternative autoregressive covariance matrix will be used instead. The Kenward-Roger approximation will be used to estimate the denominator degrees of freedom. Assuming that the data are MAR, the estimates of the treatment differences calculated from the MMRM described above are unbiased. Standard descriptive statistics will be reported for each time point on the values and changes from baseline along with the LS means, standard errors, 95% CIs and differences between treatment groups reported with LS means, standard errors, and 95% CIs.

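### The SAP's repeated-measures models omit the randomisation stratum and baseline-by-visit terms, so nominal Week 24 standard errors are probably slightly too large, and the covariance fallback is under-specified

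*SAP*

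**What the plan says.** **Randomisation.** Protocol 7.3 states: "Randomization will be stratified by scalp hair loss into one of the following two categories", namely partial loss (SALT 50 to below 95) and complete or near-complete loss (SALT 95 or above). SAP 7.2 repeats this.

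**Where the stratum is used.** The primary analysis (SAP 8.2.2) stratifies on it. For secondary responder endpoints, SAP 8.4 specifies the "Cochran-Mantel-Haenszel test using baseline scalp hair loss as the stratification factor".

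**Where it is not used.** The protocol's model for continuous endpoints (12.4.2) reads: "The model will include fixed factors for treatment group, study visit, and treatment by study visit interaction, with baseline SALT score as a covariate". The SAP keeps that form (in 8.4.1, "fixed factors for treatment group, study visit, and treatment by study visit interaction, with baseline SALT score as a covariate") and adds the endpoint's own baseline where it differs from SALT:

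| SAP section | Endpoint | Post-baseline visits | Baseline covariates | Stratum | Baseline-by-visit |
|---|---|---|---|---|---|
| 8.4.1 | Relative SALT change | 6 | SALT | No | No |
| 8.4.2, 8.4.4, 8.4.6, 8.4.9 | SPRO, CGI-S, PGI-S, QPRO items | 4 | SALT, own baseline | No | No |
| 8.4.7, 8.4.8 | BETA, BELA | 2 | SALT, own baseline | No | No |
| 8.4.10 | HADS-A, HADS-D (ANCOVA) | 1 | SALT, own baseline | No | Not applicable |

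**Covariance.** SAP 8.4: "An unstructured covariance matrix will be used to model the within-subject errors". Then: "Should the model fail to converge, an alternative autoregressive covariance matrix will be used instead". It also says: "The Kenward-Roger approximation will be used to estimate the denominator degrees of freedom". It does not say whether the autoregressive matrix has one variance or visit-specific variances, and it names no robust SE. Protocol 12.4.2 has no fallback, and SAP 13 does not list the fallback among its changes.

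**Status.** These endpoints lie outside the testing hierarchy, and their p-values are nominal (SAP 8.1.4, 8.4).

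**The concern.** Stratified randomisation balances the arms on the stratum. A model that leaves the stratum out still counts the spread between strata as residual variation, so its SE does not credit that balance. Baseline SALT captures part of this, because the stratum is a cut of baseline SALT. But its slope is forced to be the same at every visit. Early in treatment there is little change for baseline to predict. By Week 24 there may be much more, and a single slope would then fit worst at the visit of most interest.

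The fallback raises a different issue. In its plain form an autoregressive matrix has one variance for all visits. Protocol 4.4.2 describes Phase 2 improvement as building through 24 weeks, so growing spread between patients is plausible. A pooled variance would then be too small at Week 24 and too large at Week 4, and Kenward-Roger does not repair a wrong variance structure.

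At stake are the SEs, 95% confidence intervals and nominal p-values of the continuous secondary endpoints. Leaving the structure unnamed also leaves a choice open at analysis time.

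**Working it through.** **1. The plan's own figures.** The documents give no power, SD or SE for these models. The only planning figure is power for the primary endpoint (Protocol 12.1), which supplies the arm sizes 210, 350 and 140. For 8 mg versus placebo (25% versus 10%, two-sided 0.025) with continuity correction:
- difference: 0.15 − 0.5 × (1/140 + 1/350) = 0.145
- pooled SE 0.0405, unpooled SE 0.0343
- power: Φ((0.145 − 2.241 × 0.0405)/0.0343) = 94.3%, matching the stated 94%

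Without the correction it is 95.8%. For 12 mg it exceeds 99.9%. This confirms the arm sizes but says nothing about the MMRMs.

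**2. Omitted terms, unstructured matrix.** Simulation with no treatment effect, 700 patients in stratified blocks, six visits, comparing 12 mg with placebo at Week 24. Assumed, not from the documents: autoregressive correlation 0.85; 60% in the upper stratum; a baseline slope of 0.4 points per SALT point and a stratum effect of 10 or 20 points at Week 24, both growing linearly with visit. The last row sets both effects to zero.

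| SD, Week 4 to 24; stratum effect | Model SE, planned | + baseline-by-visit | + stratum-by-visit as well | SE reduction | Empirical SE, planned / full | Type I error, planned / full |
|---|---|---|---|---|---|---|
| 12 to 36; 10 | 4.07 | 3.94 | 3.93 | 3.4% | 3.89 / 3.88 | 0.043 / 0.047 |
| 12 to 36; 20 | 4.21 | 3.96 | 3.92 | 6.9% | 3.80 / 3.80 | 0.021 / 0.043 |
| 24 to 36; 10 | 4.01 | 3.93 | 3.92 | 2.2% | 3.91 / 3.92 | 0.036 / 0.047 |
| 12 to 36; no prognostic effect | 3.93 | 3.93 | 3.93 | 0% | 4.04 / 4.03 | 0.055 / 0.060 |

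The first three rows use 700 replicates, the last 200. One simulation SE on a 5% error rate is √(0.05 × 0.95/700) = 0.008, or 0.015 with 200 replicates. A separate 200-replicate run of the second row gave 0.045 and 0.080, so small differences in type I error should not be over-read.

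The baseline-by-visit term does most of the work. A stratum main effect alone moved the model SE by 0.01 or less (4.06 to 4.06 with stratum effect 10; 4.21 to 4.20 with 20).

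**3. Fallback, if read as common-variance AR(1).** With complete data, the ratio of reported to true SE at Week 24 is √(mean of the visit variances) / SD at Week 24. The nominal 5% test then runs at 2 × (1 − Φ(1.96 × ratio)). With the SD rising linearly from 1 to 3 over six visits:
- variances 1, 1.96, 3.24, 4.84, 6.76, 9; mean 4.467
- ratio √4.467/3 = 0.704
- error 2 × (1 − Φ(1.381)) = 0.167

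| Week 24 SD ÷ Week 4 SD | SE ratio at Week 24 | Nominal 5% error |
|---|---|---|
| 1 | 1.00 | 5.0% |
| 1.5 | 0.84 | 9.9% |
| 2 | 0.77 | 13.2% |
| 3 | 0.70 | 16.7% |
| 4 | 0.68 | 18.6% |

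At threefold growth the Week 4 SE is 2.11 times too large. Simulation agrees: ratio 0.74 and error 0.143 at threefold, 0.86 and 0.101 at 1.5-fold. In a 300-replicate run at threefold growth, heterogeneous AR(1) gave a ratio of 1.03, against 0.73 for common-variance AR(1).

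For the other endpoints growth runs from Week 12 to Week 24. The ratio at twofold and threefold growth is 0.77 and 0.71 with four visits, and 0.79 and 0.75 with two.

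**4. How likely is the fallback?** The unstructured matrix has 6 × 7/2 = 21 parameters for SALT, 4 × 5/2 = 10 for the four-visit endpoints and 2 × 3/2 = 3 for BETA and BELA. With about 700 patients, non-convergence looks unlikely.

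**The case against.** The strongest reply is that the planned analysis is valid and mildly conservative, and that it follows the protocol model apart from the added endpoint baselines. Baseline SALT, of which the stratum is a cut, is already in every model. All of that stands. It limits the size of the point; it does not explain why the continuous analyses drop a stratum that the responder analyses keep.

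Four stronger readings are tempting, and the documents do not support them:

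- **One common variance is the plan.** It is not. The plan is unstructured, with a separate variance at each visit. The fallback needs non-convergence, and common variance is only one reading of an unqualified term. What is documented is a missing specification.
- **Precision equivalent to extra patients is being lost.** The empirical SE of the treatment estimate barely changes when the terms are added (3.89 versus 3.88; 3.80 versus 3.80). Only the reported SE changes.
- **Every section from 8.4.2 to 8.4.9 shares the defect.** Sections 8.4.3 (CGI-I) and 8.4.5 (PGI-I) are responder analyses that do use the stratum.
- **The primary result is exposed.** Protocol 12.4.5 mentions an MMRM approach for the imputed data. But Protocol 12.4.5.1 and SAP 8.2.2 specify the stratified Mantel-Haenszel risk difference, and the SAP takes precedence (SAP 2).

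The check covers SALT most fully. Nothing in the documents shows that the stratum predicts HADS change beyond the two baselines already in that model, and no figure was computed for it.

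**Conclusion.** The point holds as a minor one, in two parts.

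**Omitted terms.** The reported Week 24 SE for relative SALT change is about 3 to 7% too large when the SD rises from 12 to 36 and the stratum effect is 10 to 20 points. The figure is about 2% with flatter SDs, and zero if neither baseline nor stratum is prognostic. Intervals are slightly wide and tests mildly conservative.

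**Fallback.** This matters only if the unstructured fit fails and the replacement is common-variance AR(1). Week 24 SEs would then be roughly 15 to 30% too small for 1.5- to 3-fold SD growth. With no growth there is no inflation. No single error rate should be quoted, because the documents give no SD at any visit.

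Both parts rest on assumed SDs, and the first also on an assumed correlation, slopes and stratum share. Both affect nominal secondary results only; the hierarchy is untouched.

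**What to change.** In SAP 8.4.1, 8.4.2, 8.4.4 and 8.4.6 to 8.4.9, add stratum, stratum-by-visit and baseline-SALT-by-visit as fixed effects. Adding the stratum as a main effect alone would achieve almost nothing in the MMRMs. In SAP 8.4.10, add the stratum to the HADS ANCOVA, for consistency with the design.

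In SAP 8.4, replace the open-ended fallback by a fixed sequence on non-convergence: heterogeneous Toeplitz, then heterogeneous AR(1). List the additions and the fallback in SAP 13.

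The cost is SAP wording before database lock and a few degrees of freedom. For the six-visit SALT model that is 5 (baseline-by-visit) + 1 (stratum) + 5 (stratum-by-visit) = 11 parameters, with about 700 patients.

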8.4.2. Secondary SPRO Endpoints

The following secondary SPRO responder endpoints will be assessed:

- Percentage of responders at Weeks 12, 16, and 20, where responders is defined as “very satisfied” or “satisfied”
- Percentage of patients achieving a ≥ 2 -point change from baseline in the SPRO scale at Weeks 12, 16, 20, and 24

In addition, the continuous secondary SPRO endpoint of change from baseline at Weeks 12, 16, 20, and 24 will be assessed with a MMRM. The model will include fixed factors for treatment group, study visit, and treatment by study visit interaction, with baseline SALT score and baseline SPRO score as covariates. Imputed values will not be used for the MMRM.

8.4.3. Clinical Global Impression of Improvement (CGI-I)

The CGI-I will be assessed by the Investigator at Weeks 12, 16, 20, and 24. Compared to the patient's alopecia areata prior to treatment at baseline, the patient's current state of alopecia areata will be assessed according to the Investigator's perceived change. The Investigator may select one of seven numeric choices representing "Very Much Worse" to "Very Much Improved". To reduce variability, one rater should perform the CGI-I assessment for the patient for the duration of the study. An example of the CGI-I assessment can be found in Appendix 17.3.2 of the protocol.

The secondary CGI-I responder endpoint of percentage of responders (defined as "much improved" or "very much improved") at Weeks 12, 16, 20, and 24 will be assessed.

8.4.4. Clinical Global Impression of Severity (CGI-S)

The CGI-S will be assessed by the Investigator and will consider the severity of the patient's alopecia areata at the time of assessment. The Investigator may select one of seven numeric choices representing "Among the most extreme hair loss" to "Normal, no hair loss". To reduce variability, one rater should perform the CGI-S assessment for the patient for the duration of the study. An example of the CGI-S assessment can be found in Appendix 17.3.1 of the protocol.

The continuous secondary endpoint of change from baseline in the CGI-S at Weeks 12, 16, 20, and 24 will be assessed with a MMRM. The model will include fixed factors for treatment group, study visit, and treatment by study visit interaction, with baseline SALT score and baseline CGI-S score as covariates.

8.4.5. Patient Global Impression of Improvement (PGI-I)

The PGI-I will be assessed by the patient at Weeks 12, 16, 20, and 24. Compared to the patient's alopecia areata prior to treatment at baseline, the patient's current state of alopecia areata will be assessed according to his/her perceived change. The patient may select one of seven numeric choices representing "Very Much Worse" to "Very Much Improved". An example of the PGI-I assessment can be found in Appendix 17.3.4 of the protocol.

The secondary PGI-I responder endpoint of percentage of responders (defined as "much improved" or "very much improved") at Weeks 12, 16, 20, and 24 will be assessed.

8.4.6. Patient Global Impression of Severity (PGI-S)

The PGI-S will be assessed by the patient and will consider the severity of his/her alopecia areata at the time of assessment. The patient may select one of seven numeric choices representing "Among the most extreme hair loss" to "Normal, no hair loss". An example of the PGI-S assessment can be found in Appendix 17.3.3 of the protocol.

The continuous secondary endpoint of change from baseline in the PGI-S at Weeks 12, 16, 20, and 24 will be assessed with a MMRM. The model will include fixed factors for treatment group, study visit, and treatment by study visit interaction, with baseline SALT score and baseline PGI-S score as covariates.

8.4.7. Brigham Eyebrow Tool for Alopecia (BETA)

The BETA is a clinician-rated scale that assesses the total eyebrow hair present. The scale is used for each eyebrow in which the Individual Eyebrow Score is derived by assessment of density (D) x surface area (SA). An expert panel will perform central readings based on photographs of the eyebrows and will provide a score for each patient with eyebrow involvement. The BETA will be performed at Baseline, Week 12, and Week 24.

The continuous secondary endpoint of change from baseline in the BETA at Weeks 12 and 24 will be assessed with a MMRM. The model will include fixed factors for treatment group, study visit, and treatment by study visit interaction, with baseline SALT score and baseline BETA score as covariates.

8.4.8. Brigham Eyelash Tool for Alopecia (BELA)

The BELA is a clinician-rated scale that assesses the total eyelash hair present. The scale is used for each eye in which the Total Eyelash Score is derived by assessment of density and distribution on the right and left eye. An expert panel will perform central readings based on photographs of the eyelashes and will provide a score for each patient with eyelash involvement. The BELA will be performed at Baseline, Week 12, and Week 24.

The continuous secondary endpoint of change from baseline in the BELA at Weeks 12 and 24 will be assessed with a MMRM. The model will include fixed factors for treatment group, study visit, and treatment by study visit interaction, with baseline SALT score and baseline BELA score as covariates.

8.4.9. Hair Quality Patient Reported Outcome (QPRO)

The QPRO questionnaire is a 4-item assessment which provides additional details on key attributes of patient hair and helps provide context to the SPRO response. Like the SPRO, the QPRO responses are on a scale of 1-5, where 1 = very satisfied, 2 = satisfied, 3 = neither satisfied nor dissatisfied, 4 = dissatisfied, and 5 = very dissatisfied. An example of the QPRO assessment can be found in Appendix 17.4.2 of the protocol.

The continuous secondary endpoints of change from baseline each individual item for QPRO at Weeks 12, 16, 20, and 24 will be assessed with a MMRM. The model will include fixed factors for treatment group, study visit, and treatment by study visit interaction, with baseline SALT score and baseline QPRO item score as covariates.

8.4.10. Hospital Anxiety and Depression Scale (HADS)

The HADS is a 14-item measure designed to assess anxiety and depression symptoms in medical patients. Items are rated on a 4-point severity scale. The HADS produces two scales, one for anxiety (HADS-A) and one for depression (HADS-D). An example of the HADS assessment can be found in Appendix 17.5 of the protocol.

The continuous secondary endpoints of change from baseline in HADS-A at Week 24 and change from baseline in HADS-D at Week 24 will be assessed with an ANCOVA. The model will include fixed factors for treatment group with baseline SALT score and baseline HADS score (HADS-A or HADS-D as appropriate) as covariates.

8.5. Other Endpoints

No other efficacy endpoints are specified.

8.6. Examination of Subgroups

No subgroup analyses are planned.

9. SAFETY EVALUATION

9.1. Overview of Safety Analysis Methods

All safety summaries will be descriptive with no statistical hypothesis testing and based on the Safety Population. Patients will be summarized according to the study drug received (ie, as treated), should it differ from the randomized treatment arm. Safety assessments will be summarized by treatment group and overall. All safety endpoints will be listed in by-patient data listings.

9.2. Extent of Exposure

Study drug exposure will be summarized for each treatment group and overall. The number of days on which study drug was dosed (at least partially), the number of days in the study, and total cumulative dose will be summarized for each treatment group.

The number of days on which study drug was dosed (at least partially) will be calculated as (treatment end date – treatment start date + 1) minus the total number of days with a dosing exception per the *Dosing Exceptions* eCRF page of partial dose (counted as 0.5 day missed), missed dose (counted as 1 day missed), or dose interruption (counted as 1 day missed). The number of days in the study will be calculated as (treatment end date – treatment start date + 1). Total cumulative dose will be calculated as the total number of tablets taken multiplied by 8 mg, 12 mg, or 0 mg for each applicable treatment.

The number and percentage of subjects with at least one dose interruption will also be summarized, where dose interruption is defined as a value of “Dose interruption” for the question “Reason for Exception” on the *Dosing Exceptions* eCRF page. The sponsor may review the free text field associated with the “Reason for Exception” prior to database lock in order to identify reasons related to the dose interruption criteria outlined in Protocol Section 9.2.1. Should these reasons be identified, the definition of dose interruption would be refined based on those findings.

Drug compliance will also be summarized, per Section 7.3.

9.3. Adverse Events

An adverse event is any untoward medical occurrence that may appear or worsen in a patient during the course of a study. It may be a new intercurrent illness, a worsening concomitant illness, an injury, or any concomitant impairment of the patient’s health, including laboratory test values, regardless of etiology. Any worsening (ie, any clinically significant adverse change in the frequency or intensity of a pre-existing condition) should be considered an adverse event. A diagnosis or syndrome should be recorded on the adverse event page of the eCRF rather than the individual signs or symptoms of the diagnosis or syndrome. A worsening of the condition under study, alopecia areata, will not be reported as an adverse event.

All patients will be monitored for adverse events during the study. Assessments may include monitoring of the following parameters: the patient’s clinical symptoms, laboratory, physical examination findings, or findings from other tests and/or procedures.

Concert Pharmaceuticals, Inc.
Statistical Analysis Plan – CP543.3001

Adverse events will be coded using MedDRA version 23.1 and summarized by treatment group, system organ class, and preferred term.

An adverse event reported after informed consent, but before the first dose of study drug (i.e., Day 1), will be considered a pre-treatment adverse event. Treatment-emergent adverse events will be defined as any adverse event that occurs after administration of the first dose of study drug. Adverse events will be limited to those collected within this protocol (ie, for rollover subjects, AEs collected under the protocol of the rollover study will not be in this study). The number and percentage of patients who report TEAEs will be summarized by treatment group, system organ class, and preferred term.

Treatment emergent adverse events will also be summarized by intensity as well as relationship to study drug.

Partial dates will be imputed for the purposes of defining TEAEs as follows:

- For a missing start day where the month and year are present, the start day will be set to the first day of the month, unless 1) the first day of the month is before the date of administration of study drug and the month and year are the same as the month and year of the date of administration of study drug, and 2) the end date is on or after the date of administration of study drug or the end date is completely missing, in which case the start day will be set to the first day of administration of study drug.
- For a missing start day and month where the year is present, the start day and month will be set to January 1st, unless 1) January 1st is before the date of administration of study drug, and 2) the end date is on or after the date of administration of study drug or the end date is completely missing, in which case the start day and month will be set to that of the first date of administration of study drug.
- For an entirely missing start date (ie day, month, and year are missing), the start date will be set to the date of administration of study drug unless the stop date is prior to the date of administration of study drug, in which case the start date will be set to the stop date.
- For a missing end day where the month and year are present, the end day will be set to the last day of the month, unless the month and year are the same as the month and year of the last visit date for the patient, in which case the end day will be set to that of the patient's last visit date.
- For a missing end day and month where the year is present, the end day and month will be set to the patient's last visit date, unless the year of the patient's last visit date is greater than the end year, in which case the end day and month will be set to December 31st.
- For an entirely missing stop date (i.e. day, month, and year are missing), the stop date will be imputed as the patient's last visit date.

Patients who report the same preferred term on multiple occasions will be counted once for the preferred term: under the highest severity when summarized by severity and under the closest relationship to study drug when summarized by relationship. Missing severity or relationship will not be imputed. If a patient reports multiple preferred terms for a system organ class, the patient will be counted only once for that system organ class.

The number and percentage of patients who experience TEAEs will be summarized by treatment group for the following:

- By system organ class and preferred term
- By severity/intensity, system organ class, and preferred term
- By relationship to study drug, system organ class, and preferred term
- Serious adverse events by system organ class and preferred term
- Serious adverse events by relationship to study drug, system organ class, and preferred term
- Adverse events resulting in discontinuation of study drug by system organ class and preferred term
- Adverse events that result in study drug dose interruption by system organ class and preferred term

Additionally, TEAEs will be summarized by time interval: 0 to 12 weeks, and 12 to 24 weeks. For each time interval, an incidence table will summarize only TEAEs with an onset date within the interval and a prevalence table will summarize all TEAEs that have an onset date within the interval or continue into the interval. Differences between the incidence and prevalence tables can provide insight into the duration of TEAEs as well as the recurrence of TEAEs. A preferred term for an individual patient will be reported in multiple time intervals if there are multiple adverse event reports. The denominator for each time interval will be the number of patients who received at least 1 dose of study drug within the interval.

By-patient listings will include all adverse events. TEAEs will be flagged.

